2. ANALYSIS POPULATION

2.1. Population Definitions

The following analysis populations will be evaluated and used for presentation and analysis of the data.

- Screening Analysis Set: All patients who signed the informed consent form.
- Safety Analysis (SA) Set: All patients who received at least 1 dose of study drug (placebo or setmelanotide). Analysis performed on the safety set will be based on patients according to treatment received.
- FAS: All patients (irrespective of age) who received at least 1 dose of setmelanotide and have baseline data.
- DUS: All patients in the FAS who demonstrate at least 5 kg weight loss (or at least 5% if baseline body weight is < 100 kg) over the first 14 weeks of active setmelanotide treatment, regardless of later disposition.

For any DUS analysis, the DUS subgroup includes:

- O Those patients initially randomized into the setmelanotide group in the double blinded, randomized, placebo-controlled period that achieved at least 5 kg weight loss (or at least 5% if baseline body weight is < 100 kg) from baseline at Week 15 visit.
- O Those patients who initially randomized in the placebo group in the double blinded, randomized, placebo-controlled period, and achieved at least 5 kg weight loss (or at least 5% if baseline body weight is < 100 kg) from week 15 (i.e., just prior to their first active dose of setmelanotide at week 15) through week 29 (i.e., after 14 weeks of active treatment with setmelanotide).
- PCS: All randomized patients who received at least 1 dose of placebo or setmelanotide and have baseline data. This population is specifically defined for the 14-week placebo-controlled, double-blind period (Period 1). Analysis performed on PCS will be based on subjects as randomized.
- Per-Protocol Set at End of Period 1 (PP at EOP1): All subjects in PCS without any major protocol violations that will result in exclusion of the subjects from the analysis.
- Per-Protocol Set at End of Period 2 (PP at EOP2): All subjects in FAS without any major protocol violations that will result in exclusion of the subjects from the analysis.
- Completers Set (CS): all subjects in the PP at EOP1 population who continue on active treatment or placebo to complete a full 14-week placebo-controlled double blinded period (Period 1)

The FAS population is the primary population for the analysis of efficacy endpoints. The DUS population may be used for sensitivity analyses of efficacy endpoints, as appropriate.

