By nature of the study design (as introduced above in Section 1.2), a small percentage of patients who are randomized into the placebo arm may have less than ~52 weeks of setmelanotide treatment by the timing of the primary analysis (when the last patient enrolled has completed Period 2). Hence, the primary analysis will include a multiple imputation (MI) model (SAS PROC MI) that will be used to impute the measurements for patients with less than ~52 weeks of setmelanotide treatment to a timepoint that approximates 52 weeks of setmelanotide treatment. The final multiple imputed datasets will be analyzed using Rubin's rule (with SAS PROC MIANALYZE).

Due to the relatively small number of observation (i.e., number of patients) and large number of the visits (~15 protocol specified visits), there may not be enough observations to fit regression models in the multiple imputation. Therefore, protocol specified visits will be combined as appropriate, and the averaged values (across the combined visits) per the new derived Visit Categories (VC) will be used in the regression in the multiple imputation (SAS PROC MI). The multiple imputation model will contain the following new visit categories (VC) derived as follows:

- VC1=Average (V1, V2)
- VC2=Average of Scheduled Visits between VC1 and VC3
- VC3=Visit Occurring Closest to Day 98/14 Weeks within analysis window
- VC4=Average of Scheduled Visits between VC3 and VC5
- VC5=Visit Occurring Closest to Day 365/52 Weeks within analysis window
- VC6=Average of Scheduled Visits between VC5 and VC7

27

• VC7=Visit Occurring Closest to Day 462/66 Weeks within analysis window

Note, Early Termination visits will be treated as scheduled visits and may slot into any VC as fits criteria. Further, imputation of weight for 52 week analysis will focus on VC5 (for subjects initiated on active treatment) and VC7 (for subjects initiated on placebo) as these VCs are identified similarly, if not exactly, as the true timepoint would be identified, if it were not missing.

The above planned combination of the visits may be adjusted if the model cannot be fitted due to small sample size. Details will be defined in the ADRG.

Once VCs are identified, they will be time aligned by treatment arm before multiple imputation occurs.

That is, subjects initially randomized into the active treatment arm will have:

- VC1
- VC2
- VC3
- VC4
- VC5 (52 Weeks on Active Treatment)

While subjects initially randomized into the placebo arm will have:

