
- VC3
- VC4
- VC5
- VC6
- VC7 (52 Weeks on Active Treatment)

Monotone regression will then be used to impute the missing values, assuming proper missingness structure. The monotone regression method will impute 100 datasets. A seed of 2187 has been randomly generated and will be used.

Fully conditional specification (FCS) regression may be used in the case that monotone regression is deemed not appropriate.

Daily hunger scores will have weekly average hunger score calculated and these weekly averages mapped to Visit Categories with the same algorithm as above.

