3.10.3. Approach on Missing Value in ~14-Week Placebo-Controlled, Double-Blinded Period (Period 1)

Patients may have missing values in Period 1 for many reasons such as drop out, early discontinuation, missed visits, or AEs etc. Missing values in this period will be imputed with a similar MI approach as 52 week analysis as defined in the primary imputation approach.

However, as this analysis revolves around 14 week timepoint, VC3 will be the focus of the imputation model. VC1, VC2, and VC3 will used in the multiple imputation model (SAS PROC MI) for 14 week timepoint with treatment group as a class factor. A sensitivity analysis may be conducted based on treatment failure approach on the missing value imputation for this period as appropriate.

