- Example 3: A patient who was initially randomized to placebo in Period 1 but may have been in the study for only 10 months, having received 3 months placebo then 7 months of active setmelanotide. The patient's primary endpoint will be defined as the patients ~12 months active treatment measurement as generated via multiple imputation method described above, since the patients active setmelanotide treatment duration is less than 10 months.
- Example 4: A patient who was initially randomized to placebo in Period 1 but may have been in the study for 14 months, having received 3 months placebo then 11 months of active setmelanotide. The patient's primary endpoint will be defined as the closest done to 52-weeks of active treatment within the 10-14 months window.

There are two planned visits in Period 3 (14-week open-label treatment): Visit 14 (~Week 60) and Visit 15 (EOS, ~Week 66). The analyses and summaries on data collected in this period will not be a main priority of the primary analysis for NDA submission or analyses in other regulatory agencies. However, an additional supportive analysis may be provided on these data after the approximately last patient in pivotal cohort completes the last visit at the end of period 3.

The additional supportive analysis and summary at end of period 3 will be based on relative visits/days (i.e., staggered alignment) from the first dose of the setmelanotide, below examples illustrate the staggered alignment for analysis,

- V2 (Week 1) of patients initially randomized in setmelanotide group (planned first dose visit of setmelanotide) will align with V6 (Week 15) of patients initially randomized in placebo group (i.e, planned first dose visit of setmelanotide).
- V13 (Week 53) of patients initially randomized in setmelanotide group (~52 week visit on setmelanotide) will align with V15 (Week 66) of patients initially randomized in placebo group (i.e, ~52 weeks visit on setmelanotide).
- Other visits will be aligned in a similar fashion.

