4.3. Efficacy Analyses

In general, efficacy analyses will be conducted using the FAS population. Additional supportive analysis based on the DUS, CS, and/or PP Sets etc. may be provided as appropriate. Unless stated otherwise, all the analysis on hunger score data will be based on patients ≥12 years of age while only descriptive summary will be provided for patients <12 years of age (due to the different hunger score questionnaire tools). Descriptive statistics for endpoints analyzed at ~52 weeks will have their visits aligned by approximate relative day on setmelanotide (active treatment visit).

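### The 52-week imputation pairs visits said to be time aligned, but three of the five pairs differ in weeks on setmelanotide, which can overstate weight loss in imputed patients who began on placebo

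*SAP*

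**What the plan says.** SAP 3.10.1 imputes the 52-week value for patients who began on placebo and have too little time on setmelanotide at the data cut. Because the sample is small, visits are collapsed into seven categories defined on study day, for example "VC3=Visit Occurring Closest to Day 98/14 Weeks within analysis window" and "VC5=Visit Occurring Closest to Day 365/52 Weeks within analysis window". The even-numbered categories average the scheduled visits in between. The section then states: "Once VCs are identified, they will be time aligned by treatment arm before multiple imputation occurs". The setmelanotide arm contributes VC1 to VC5 and the placebo arm VC3 to VC7. The only on-drug time given is for the last position, VC5 in one arm and "VC7 (52 Weeks on Active Treatment" in the other. Monotone regression then fills the gaps in 100 datasets, and weekly hunger averages use the same mapping.

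For this 52-week model the SAP mentions neither a treatment term nor imputation separately by arm. For the Period 1 model (SAP 3.10.3) it does: the categories are used "for 14 week timepoint with treatment group as a class factor".

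Elsewhere the SAP counts time from first setmelanotide dose:
- SAP 4.3: "Descriptive statistics for endpoints analyzed at ~52 weeks will have their visits aligned by approximate relative day on setmelanotide (active treatment visit".
- SAP 2.1: the Designated Use Set follows ex-placebo patients "through week 29 (i.e., after 14 weeks of active treatment with setmelanotide".
- SAP 3.11.1: the supportive end-of-Period-3 analysis "will be based on relative visits/days (i.e., staggered alignment) from the first dose of the setmelanotide".

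**The concern.** Moving two categories along is not the same as moving 14 weeks along, because the categories cover very different lengths of time. The pairing is right at the start and the end and wrong in between. If one regression is fitted to both arms without a treatment term, it treats an ex-placebo patient at on-drug week 38 as if at the same stage as a setmelanotide patient at on-drug week 14.

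The imputed values enter the primary responder rate and the key secondary percent changes. If patients keep losing weight after week 14, the error favours the drug. The non-replacement sensitivity analysis in SAP 4.3.4 uses the same imputed values and so cannot reveal it.

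**Working it through.** **Inputs.** Visit days are from SAP Tables 1 and 2: V2 = 1, V3 = 15, V4 = 43, V5 = 71, V6 = 99, V7 = 113, V8 = 155, V9 = 197, V10 = 239, V11 = 281, V12 = 323, V13 = 365, V14 = 414, V15 = 462. Setmelanotide starts on day 1 in the setmelanotide arm and at V6 (day 99) in the placebo arm. Weight is assumed to be measured at every clinic visit, because the weight row is not visible in the published schedule.

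**Formula.** On-drug week = (study day − 1)/7 for setmelanotide and (study day − 99)/7 for ex-placebo, averaged over the visits in a category.

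**The plan's own figure.** The last position is labelled 52 weeks in both arms: (365 − 1)/7 = 52.0 and (462 − 99)/7 = 51.9. The label reproduces.

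**All five positions.**

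| Position | Setmelanotide | On-drug weeks | Ex-placebo | On-drug weeks | Gap |
|---|---|---|---|---|---|
| 1 | VC1 | 0 | VC3 | 0 | 0 |
| 2 | VC2 (V3–V5) | 2, 6, 10; mean 6 | VC4 (V7–V12) | 2, 8, 14, 20, 26, 32; mean 17 | 11 |
| 3 | VC3 (V6) | 14 | VC5 (V13) | 38 | 24 |
| 4 | VC4 (V7–V12) | 16, 22, 28, 34, 40, 46; mean 31 | VC6 (V14) | 45 | 14 |
| 5 | VC5 (V13) | 52.0 | VC7 (V15) | 51.9 | 0.1 |

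Three of five do not match. The schematic in the protocol puts V14 at Week 59 rather than 60; position 4 mismatches either way.

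**Direction.** The cut falls when the last enrolled patient completes Period 2, so an administratively cut ex-placebo patient's last value is typically V13, in position 3. After position 3 the setmelanotide arm has 52 − 14 = 38 weeks to go and this patient has 52 − 38 = 14. A pooled model learns the change largely from the former and applies it to the latter.

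**Patients affected.** Missing values for other reasons are reset to baseline (SAP 3.10.2). The primary window is 40–56 on-drug weeks (SAP 3.11.1). For ex-placebo patients V13 (week 38) is outside it and V14 (week 45) inside, so only those enrolled in about the last (414 − 365)/7 = 7 weeks are imputed. Expected number = 7/(enrolment weeks) × 0.5 × number aged ≥12. Assuming even enrolment over 9–24 months and 26–34 patients aged ≥12, this gives:
- low: 7/104 × 0.5 × 26 = 0.9
- middle (12 months, 30 patients): 7/52 × 0.5 × 30 = 2.0
- high: 7/39 × 0.5 × 34 = 3.1

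**Bias by simulation.** Assumed: 15 per arm, mean 52-week loss 7%, SD 7, within-person drift SD 2% at 52 weeks, visit noise 0.7%; monotone Bayesian regression, 300–600 trials of 20 imputations.
- SAP categories, no treatment term, continuing loss (time constant 12–30 weeks, or linear), 2–4 imputed: loss overstated by 1.0–2.6 points and responder probability by 6–16 points per imputed patient. Example, linear loss with 2 imputed: true probability 0.31, imputed 0.47.
- Other shapes, overstatement of loss: time constant 6 weeks, 0.3–0.4 points; plateau at week 14, about 0.1; nadir at week 14 then regain, 0.0–0.1; nadir at week 30 then regain, 0.7–0.8.
- SAP categories with a treatment term: loss within 0.2 points, responder probability +1 to +4 points.
- Five categories on drug time: loss within 0.2 points, responder probability within about 1 point.

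Effect on the overall rate of 30 patients under continuing loss: +0.3 to +0.5 points with 1 imputed, +0.4 to +1.1 with 2, about +1 to +1.5 with 3. In the linear example, 16 × 2/30 = 1.1.

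A second set of assumptions (16 per arm, mean loss 8%, SD 8, visit noise 1%, 2–6 imputed) gave 0.9–3.4 points of loss and 0.3–2.8 points on the overall rate under continuing loss, and about 0.2 points of loss with a week-14 plateau.

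**Success decision.** With a 20-week time constant and 2–3 imputed, rejection rates under the SAP imputation and under complete data were 0.005–0.007 for both at a true rate of 10%, 0.50 and 0.50–0.51 at 25%, and 1.00 for both at 66%.

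**The case against.** The bias needs a model that the SAP does not spell out. It lists the categories arm by arm; if each arm were imputed separately, the positions would never mix, and a treatment term nearly removes the bias in the mean. The shift in the overall rate is less than half a patient, since one in 30 is 3.3 points, and the decision does not change. Enrolment pace, age mix and trajectories are assumed. Hunger was not simulated, and protocol 3.4 expects a fast hunger effect, which is the case with little bias. The drug-time rules in SAP 2.1, 4.3 and 3.11.1 govern other analyses. A completers' analysis that drops these patients is already described.

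Much of this stands as limits: the small reach, the unchanged decision, the assumed sizes and the absence of any hunger result. It does not remove the point. Aligning the arms has little purpose unless they share one model, and the SAP's worry about too few observations makes separate models by arm less likely. If a treatment term is intended, it has to be written down, as it is for the 14-week model. The rules elsewhere do not bind the imputation, but they show which clock the SAP uses for 52-week efficacy. The completers' analysis is optional.

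**Conclusion.** The concern holds. The mismatch at positions 2, 3 and 4, by about 11, 24 and 14 weeks, follows from the SAP's own visit days and needs no assumption. The bias is conditional on a pooled model without a treatment term and on loss continuing after on-drug week 14. Its direction was the same in every continuing-loss shape tried; its size rests on the assumptions listed. For the expected 1–3 affected patients the responder rate is overstated by roughly 0.3–1.5 points. This should be fixed because it affects the reported estimates of a pivotal trial, not because it threatens the test against 10%.

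**What to change.** Keep five categories but define them in both arms by weeks since first setmelanotide dose:

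| Category | Setmelanotide | Ex-placebo | On-drug weeks |
|---|---|---|---|
| 1 | baseline | baseline | 0 / 0 |
| 2 | V3–V5 | V7–V8 | mean 6 / 5 |
| 3 | V6 | V9 (Week 29) | 14 / 14 |
| 4 | mean of V10 and V11 | V13 | 37 / 38 |
| 5 | V13 | V15 | 52 / 51.9 |

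This grouping leaves some visits out. A fourth category that averages V7–V12 (mean week 31) against V10–V13 (mean week 29) also performed well, within about 0.5 points of the true mean loss in every shape tried under the second set of assumptions. What matters is one clock for both arms. Use the same mapping for weekly hunger averages.

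State whether treatment group is in the 52-week model. A treatment term alone, with the present categories, would leave responder probability 1–4 points high. Make the Active Treatment-Completer's analysis in SAP 4.3.4 mandatory.

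The cost is SAP wording and the visit mapping in one program, with no new data and no extra category. The reported responder rate may come out slightly lower.

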3.10.2. Approach on Missing Value Due to Other Reasons for ~52 Weeks Analysis

Every effort should be made to avoid missing values, but patients may have missing values due to other reasons such as lost to follow up, early dropout/discontinuation, missed visit, AEs etc. in addition to the administrative reason by the nature of the study design as described above. In these cases, the same principal and MI approach will be used for imputation of the missing value as outlined above. However, for the primary and key secondary analyses, these imputed values will then be replaced with the patient's baseline

value. This constitutes a treatment failure approach for these patients as the effective change and percent change from baseline will equate to 0. To assess the robustness of the analysis, a sensitivity analysis will also be conducted based on the imputed values themselves (no baseline replacement). For analyses outside of the primary and key secondary analyses, handling may differ based upon the analysis specified. Endpoints/analyses requiring imputations that are closely related to the primary or key secondary analyses will utilize the same handling as the primary and key secondary endpoints (baseline replacement). Other analyses utilizing imputation that are not closely related to the primary or key secondary analyses will utilize the values generated via multiple imputation and will not be replaced with baseline values. The specific handling for these analyses will also be outlined in the appropriate section below.

3.10.3. Approach on Missing Value in ~14-Week Placebo-Controlled, Double-Blinded Period (Period 1)

Patients may have missing values in Period 1 for many reasons such as drop out, early discontinuation, missed visits, or AEs etc. Missing values in this period will be imputed with a similar MI approach as 52 week analysis as defined in the primary imputation approach.

However, as this analysis revolves around 14 week timepoint, VC3 will be the focus of the imputation model. VC1, VC2, and VC3 will used in the multiple imputation model (SAS PROC MI) for 14 week timepoint with treatment group as a class factor. A sensitivity analysis may be conducted based on treatment failure approach on the missing value imputation for this period as appropriate.

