8.4. Timing of Analyses

By nature of the study design, a small percentage of patients who are randomized into the placebo arm may have less than ~52 weeks of setmelanotide treatment by the timing of the primary analysis (end of Period 2); hence, a linear model based extrapolation will be used to impute their measurements after ~52 weeks setmelanotide treatment for the primary analysis. In general, missing values unrelated to study treatment (eg, due to lost to follow-up or missed visit) will also be imputed with the linear model based extrapolation, but missing values due to treatment-related reasons (eg, lack of efficacy or AEs) will be imputed as treatment failures. A data snapshot will be taken for the primary analysis.

Once the study is complete (ie, the last patient has completed his/her last visit), the database will be locked and a supplemental supportive analysis will be provided.

No formal interim analysis is currently planned for this study.

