8.5.2.2. Other Secondary Efficacy Analyses

The analysis on these other secondary efficacy endpoints will be performed based on patients \geq 12 years of age at baseline.

 Mean percent change from baseline in body weight (in patients ≥12 years of age at baseline) at the Week 14 visit compared with placebo.

The analysis on this secondary endpoint will be a between group comparison, based on a two-sample rank test, at a 1-sided 0.05 significance level. The 2-sided 90% CI will be provided. The analysis will be based on ≥12 yo FAS. The similar analysis strategy and missing value handling approach that are described in Section 8.4 will be used while change from baseline will be imputed as 0 for treatment failures.

The proportion of patients who achieve a ≥25% improvement in the weekly average of the
daily hunger score (in patients ≥12 years of age at baseline) at the Week 14 visit compared
with placebo.

The between-group comparison on the proportion of patients who achieve a $\geq 25\%$ improvement in the weekly average of the daily hunger score at the Week 14 visit will be conducted with a unconditional exact binomial test, at a 1-sided 0.05 significance level. The 2-sided 90% CI will be calculated using the exact Clopper-Pearson method for each group. The analysis will be based on the ≥ 12 yo FAS. The similar analysis strategy and missing value handling approach that are described in Section 8.5.1 will be used.

 Mean percent change from baseline in the weekly average of the daily hunger score (in patients ≥12 years of age at baseline) at the Week 14 visit compared with placebo.

The between-group comparison, analysis strategy and missing value handling approach on this endpoint will be conducted with the same approach as the one used for the mean percent change from baseline in body weight at the Week 14 visit compared with placebo.

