[figure not shown]
In order to look at the impact of missing hunger data, a sensitivity analysis may be done to examine if there are any differences in conclusions drawn by data availability; analysis for daily hunger scores will be repeated for patients with at least 3 of 7 days of data present. No imputations will be made for missing data.

[figure not shown]
Treatment Failure Analysis:

In order to look at the impact of missing data on the comparisons between setmelanotide-treated patients and placebo patients after ~14 weeks of treatment, a sensitivity failure analysis may be done. For the non-key, secondary endpoints, patients who have missing 14 week data will be considered treatment failures. Similar to the secondary analyses, this sensitivity analysis will be based on a two-sample t-test for each of the 100 imputed datasets. The outcomes from the 100 imputed datasets will be combined using Rubin's Rule to provide a p-value and corresponding confidence intervals.

Statistical Analysis Plan, Protocol RM-493-023 29 October 2020, Version 3.0

Table 3 Summary of Core Analysis Elements

Endpoints	Analysis Set (1) Primary (Sensitivity)	Main Patient Group	Baseline ⁽²⁾	Subgroup Analysis
Primary				
Proportion of patients who achieve a \geq 10% reduction from baseline in body weight after ~52 weeks of treatment	FAS (SH, AG, PP at EOP2)	≥12 years old	ATB	BBS, AS, <12 yo, <17 yo
Key Secondary (after ~52 weeks of treatment)				
Mean percent change from baseline in body weight	FAS (DUS)	≥12 years old	ATB	BBS, AS, <12 yo, <17 yo
Mean percent change from baseline in the weekly average of the daily hunger score	FAS (FAS: 3/7 daily	≥12 years old	ATB	BBS, AS, <12 yo
	responses, DUS)			
Proportion of patients who achieve a $\geq 25\%$ improvement in the weekly average of the daily hunger score	FAS (FAS: 3/7 daily responses)	≥12 years old	ATB	BBS, AS
Secondary (at the Week 14 visit)				
Mean percent change from baseline in body weight after treatment with setmelanotide as compared with placebo	PCS (PP at EOP1, CS)	≥12 years old	PCPB	BBS, AS, <12 yo, <17 yo
Mean percent change from baseline in the weekly average of the daily hunger score after treatment with setmelanotide as compared with placebo	PCS (PP at EOP1, CS, PCS: 3/7 daily responses)	>12 years old	PCPB	BBS, AS, <12 yo

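### Week-14 values missing because of adverse events or lack of efficacy are filled in from a same-arm model in the main analysis, not scored as failures, which can overstate the two contrasts with placebo

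*SAP*

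**What the plan says.** SAP 3.10.3 first lists why Week-14 data may be absent: "Patients may have missing values in Period 1 for many reasons such as drop out, early discontinuation, missed visits, or AEs etc". It then applies one method to all of them: "Missing values in this period will be imputed with a similar MI approach as 52 week analysis as defined in the primary imputation approach". The model uses visit categories VC1, VC2 and VC3 "for 14 week timepoint with treatment group as a class factor". No baseline replacement follows. The failure approach appears only as an option: "A sensitivity analysis may be conducted based on treatment failure approach on the missing value imputation for this period as appropriate". SAP 4.3.4, also optional, describes it as follows: "For the non-key, secondary endpoints, patients who have missing 14 week data will be considered treatment failures". That wording makes no distinction by reason.

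The supplied protocol has another rule. Under 8.4, "missing values due to treatment-related reasons (eg, lack of efficacy or AEs) will be imputed as treatment failures", while unrelated missing values are extrapolated with a linear model. Section 8.5.2.2 carries this to the Week-14 means: "change from baseline will be imputed as 0 for treatment failures".

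At ~52 weeks, SAP 3.10.2 imputes values missing for non-administrative reasons and then overwrites them with baseline, for the primary and key secondary analyses. It adds: "Endpoints/analyses requiring imputations that are closely related to the primary or key secondary analyses will utilize the same handling".

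**The concern.** The Week-14 contrasts in weight and hunger are the trial's only randomised comparisons with placebo. An imputation model with treatment arm as a factor predicts a lost setmelanotide patient's Week-14 value from that patient's own early values and from setmelanotide patients who were still observed. If the patient left because of an adverse event or lack of efficacy, the prediction usually still credits some drug benefit. The SAP scores the same kind of patient as a failure at ~52 weeks and does not explain the difference.

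Protocol 1.4.2.2 lists nausea, vomiting, diarrhoea and fatigue among events more frequent on setmelanotide than placebo. Losses through adverse events could therefore fall more on the active arm, and the imputation rule would then favour the drug.

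**Working it through.** **No plan figure to reproduce.** The documents give no Week-14 effect, SD, dropout rate or power. The only power figures (7 patients, ~95% and ~91%) belong to the primary endpoint and play no part here.

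**Inputs from the documents.** The pivotal cohort has 38 patients (SAP 1.1.1) randomised 1:1, so about 38/2 = 19 per arm at all ages. That is roughly a ceiling for patients aged 12 or over, whose number is not stated. The Week-14 window is ±4 weeks (SAP 3.11.2).

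**Assumptions.** 13 to 19 patients per arm; 1 to 3 setmelanotide patients with treatment-related missing values; weight change on drug of -3% to -7%; placebo change of +1% to -2%.

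**Step 1, closed form.** Let dT and dP be the shares missing on drug and placebo, and muT and muP the mean percent changes. If imputed values equal the arm mean:

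(zero-scored difference) - (imputed difference) = dP × muP - dT × muT

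A positive result means that imputation is more favourable to drug. With 15 per arm, two drug patients missing, -5% on drug and 0% on placebo, this is (2/15) × 5 = 0.67 points: -5.00 imputed against -4.33 zero-scored. Over the assumed ranges, with losses on drug only, the gap runs from 3/19 = 0.16 to 3 × 7/13 = 1.62 points.

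With placebo at zero, the excess relative to the zero-scored estimate is k/(n-k) for k missing drug patients:

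| n per arm | k=1 | k=2 | k=3 |
|---|---|---|---|
| 19 | 1/18 = 5.6% | 2/17 = 11.8% | 3/16 = 18.8% |
| 15 | 1/14 = 7.1% | 2/13 = 15.4% | 3/12 = 25.0% |

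**Step 2, use of the patient's own early weights.** The model also conditions on VC1 and VC2. VC2 averages the visits between baseline and Week 14, so an early leaver's VC2 holds only the first visits and predicts a smaller loss. A simulation regressed Week 14 on treatment and VC2, with leavers losing weight typically up to Week 6 and then unobserved, between-patient SD 3% and residual SD 0.7%. The excess over zero-scoring was:

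| n per arm | k=1 | k=2 | k=3 |
|---|---|---|---|
| 19 | about 4% | about 8% | about 13% |
| 15 | about 5% | about 11% | about 17% to 18% |

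The result was the same for an assumed loss of 3% or 5%.

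**Step 3, who leaves.** A second simulation (15 per arm, SD 4, -5% against 0%) compared two patterns of drug-arm loss:

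| Drug patients missing | k | Imputed | Zero-scored | Excess |
|---|---|---|---|---|
| At random | 2 | -4.99 | -4.30 | 4.99/4.30 - 1 = 16% |
| Poorest responders | 2 | -5.13 | -5.01 | 5.13/5.01 - 1 = 2% |
| Poorest responders | 3 | -5.38 | -5.03 | 5.38/5.03 - 1 = 7% |

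**Step 4, losses on placebo.** Take one drug and three placebo failures, 15 per arm, in the closed form.
- Weight, -5% and -2%: (1/15) × 5 - (3/15) × 2 = -0.07, so -3.00 imputed against -3.07 zero-scored.
- Hunger, -30% and -20%: (1/15) × 30 - (3/15) × 20 = -2, so -10 imputed against -12 zero-scored.

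Here imputation is the less favourable rule for the drug.

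**The case against.** **Few values may need imputing.** Patients who stop drug are urged to attend the remaining visits (Protocol 4.5, SAP 3.9). Protocol 6.1 allows home visits or telephone follow-up, and Early Termination visits enter the visit categories (SAP 3.10.1). VC3 is the visit nearest Day 98 within the window. The Week 11 visit on Day 71 is 98 - 71 = 27 days away, inside 28 days, and qualifies. Imputation is then confined largely to patients with no value from about Day 70 on. This stands and limits the size.

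**The direction is not fixed.** Lack of efficacy may drive patients off placebo, and Step 4 shows the reversal. This stands too.

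**A reader might infer that leavers are treated as if they had stayed on drug.** The model uses each patient's own early values, so poor responders are predicted to do poorly (Step 3). The inference goes too far, although some benefit is usually still credited.

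**A reader might infer that the SAP contradicts itself through its clause on closely related analyses.** That clause sits in the section on ~52 weeks, which also allows other analyses to differ and defers to later sections. Section 3.10.3 is the specific rule for Period 1. There is no contradiction, only an unexplained difference.

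**A reader might infer a breach of the protocol.** The SAP says that it supersedes the protocol and cites a version dated 26 August 2020. The supplied protocol has about 30 patients, four key secondary endpoints and 1-sided 0.05, and appears to be a different version. The change may be deliberate.

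**The stakes are limited.** The Week-14 endpoints are other secondary endpoints, outside the success criterion and the step-down order. Failure scoring is conservative in a one-sample test against a fixed value but need not be so between two arms. Both points are fair, and they argue for a modest change.

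**Conclusion.** The concern holds in conditional form. The main Week-14 analysis makes no distinction by reason for missingness, is milder than the SAP's own ~52-week rule and the supplied protocol's Week-14 rule, and has only an optional, undivided failure analysis beside it. If treatment-related missing values fall mainly on setmelanotide and placebo change is near zero, the two contrasts can be overstated relative to failure scoring. The excess is about 4% to 18% for one to three such patients with 15 to 19 per arm, assuming a typical early loss and then zero change. It reaches 25% if imputed values equal the arm mean, and falls to about 2% for two patients who were already the poorest responders.

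The documents do not support the flat statement that the effect is overstated. They give no dropout rate, the gap is nil without treatment-related missing values, and it can reverse. Zero change is also a scoring convention, not an observed outcome. No p-value was calculated, so nothing is claimed about significance.

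**What to change.** In SAP 3.10.3 and 4.3.3, for both arms:

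- When the Week-14 value is missing for a treatment-related reason (adverse event or lack of efficacy), replace the imputed value with the placebo-controlled period baseline value, that is 0% change, in each of the 100 datasets.
- Keep multiple imputation for unrelated missing values, such as a missed visit or loss to follow-up.
- Use observed values for patients who stop drug but attend.
- Report the all-imputation analysis as a sensitivity analysis that *will*, not *may*, be done, and amend 4.3.4 to match.
- State the intended Week-14 estimand, and classify reasons for missing values before treatment codes are released to the study team.

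At minimum, keep the present main analysis, make a failure analysis split by reason mandatory, and report it beside the imputation result.

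The cost is SAP wording and one replacement step already specified for ~52 weeks. Withdrawal reasons are already recorded in the eCRF (Protocol 4.5, SAP 3.9). The estimated effect and the power may change slightly, usually downwards.
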